3.9 Screen Failures

Since the core component of this trial is a 6-month safety follow-up trial, no subject will be considered a screen failure.

3.10 Definition of Completed Subjects

The core safety follow-up component of the trial is defined as the time period during which subjects are evaluated for primary and/or secondary objectives of the trial regardless of whether or not the subject was on tolvaptan treatment. For purposes of this trial, subjects who complete the Month 6 visit in the core safety component will be defined as trial completers.

The opportunity to participate in the optional tolvaptan treatment component is open to subjects during their 6-month participation in the core safety component.

3.11 Definition of Lost to Follow-up

Subjects or subjects' parents/guardians who cannot be contacted on or before their final visit prior to the trial termination date, who do not have a known reason for discontinuation (eg, withdrew consent or AE), and for whom a current health status at the end of the trial cannot be determined will be classified as "lost to follow-up" as the reason for discontinuation. Current health status can be determined from a variety of sources, either by obtaining acceptable documentation for death (ie, death certificate, medical records, public records, or statement by a family member or primary care physician) or acceptable documentation for life (ie, direct contact with the subject, medical records, successful telephone call with the subject, statement by a family member or primary care physician, or public records). It is expected that 3 documented attempts will be made to determine a subject's current health status before assigning a "lost to follow-up" status.

3.12 Subject Compliance

For the core safety follow-up component compliance is defined as completion of all visits.

For the optional tolvaptan treatment component compliance will be ensured by watching the subject take his/her tolvaptan while the subject is hospitalized or during clinical trial site visits. For nonclinical trial site days, compliance will be assessed by the number of tablets remaining when the subject returns the blister cards at the next visit. This information will be recorded on the appropriate eCRF and on the Drug Accountability Forms.

3.13 Protocol Deviations

In the event of a significant deviation from the protocol because of an emergency, accident, or mistake (eg, violation of informed consent/assent process, tolvaptan dispensing or subject dosing error, treatment assignment error, or subject enrolled in violation of eligibility criteria or concomitant medication criteria), the investigator or designee will contact INC Research at the earliest possible time by telephone. The investigator and sponsor will come as quickly as possible to a joint decision regarding the subject's continuation in the trial. This decision will be documented by the investigator and the sponsor, and reviewed by the site monitor.

4 Restrictions

4.1 Prohibited Medications

During tolvaptan treatment, continuous or short term use of other medications, while not prohibited, may be restricted by the investigator because of their potential for interference with tolvaptan metabolism. Since tolvaptan is a sensitive CYP3A4 substrate, subject dosing will be determined based on weight, age and use of CYP3A4 inhibitors. Refer to [Section 3.2.1](#) for dosing guidelines. A partial list of CYP3A4 inhibitors is provided in [Table 4.1-1](#).

boceprevir	nefazodone
clarithromycin	nelfinavir
clotrimazole (oral)	posaconazole
conivaptan	ritonavir
indinavir	saquinavir
itraconazole	telaprevir
ketoconazole	telithromycin
lopinavir	voriconazole
mibefradil	

4.2 Other Restrictions

The ingestion of pomelo, grapefruit, grapefruit juice, products containing Seville oranges, and St. John's Wort is prohibited from 72 hours prior to dosing with tolvaptan until 24 hours post-last dose of tolvaptan. In addition, the use of alcohol within 72 hours prior to dosing and during tolvaptan treatment is prohibited.

The use of saline in this population should be closely monitored. The use of hypertonic saline (3% or greater) within 8 hours of the initial screening laboratory collection prior to tolvaptan treatment is prohibited. The use of hypertonic saline (3% or greater) is prohibited during tolvaptan treatment. Routine use of hypertonic saline, while prohibited, may be considered only if used emergently (ie, with a severe symptomatic episode) and with the understanding that free water clearance may be stimulated if tolvaptan had been administered in the prior 24 hours, based on the medical judgment of the investigator. Please see [Section 4.1](#) for the partial list of prohibited medications during tolvaptan treatment. The use of normal saline (0.9%) is allowed during the Pretreatment baseline Period until the beginning of treatment; normal saline use can resume during the follow-up period. Subjects should no longer be on maintenance fluids containing normal saline during treatment with tolvaptan. Subjects may be administered IV solutions containing hypotonic saline (eg, half-normal [0.45%] saline) if necessary, for fluid management. The medical monitor should be contacted at any point if questions arise regarding the use of saline during the trial.

5 Reporting of Adverse Events

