3.2.1.2 Titration Guidelines for the Optional Tolvaptan Treatment Component

In the optional tolvaptan treatment component of the trial, eligible subjects will receive tolvaptan based on age, weight, and the use of CYP3A4 inhibitors. Tolvaptan tablets will be administered orally QD, preferably in the morning hours.

Tolvaptan doses can be titrated QD and will be based on serum sodium levels assessed at 24 (\pm 4) hours following initiation of therapy and each subsequent dose. Titration guidelines are detailed in [Figure 3.2.1.2-1](#). Titration must occur in a hospital setting. Titration may not occur within 24 (\pm 4) hours of the previous dose and must be based on serum sodium assessment obtained $>$ 20 hours post previous dose. Titration is limited to no more than twice the previous dose, and will be limited to the maximum dose per body weight.

An age-appropriate formulation is not available for this trial. Therefore, the following subjects will be excluded from the optional treatment component of this protocol:

- Subjects $<$ 4 years of age, or weighing $<$ 10 kg,
- Subjects with an inability to swallow tablets, and
- Subjects weighing $<$ 20 kg and taking a moderate or potent CYP3A4 inhibitor

[Table 3.2.1.2-1](#) outlines starting tolvaptan doses and adjustments when tolvaptan is administered concurrently with potent or moderate CYP3A inhibitors. Tolvaptan doses will be reduced 75% and 50% if a potent or moderate inhibitor, respectively, is being concurrently administered.

Table 3.2.1.2-1 Starting Tolvaptan Doses With or Without Potent or Moderate CYP3A4 Inhibitors				
Age/Weight	Can subject swallow a tablet?	Starting Dose: No CYP Inhibitor	Starting Dose: Moderate CYP Inhibitor	Starting Dose: Potent CYP Inhibitor
≥ 4 y AND ≥ 10 to < 20 kg	Yes	3.75 mg	Not eligible for treatment	Not eligible for treatment
≥ 4 y AND ≥ 20 to ≤ 50 kg	Yes	7.5 mg	3.75 mg	Not eligible for treatment
≥ 4 y AND > 50 kg	Yes	15 mg	7.5 mg	3.75 mg

Based on the weight versus dose information provided in [Table 2.2-1](#) and taking into consideration the concomitant use of a CYP3A4 inhibitor, the starting doses are as follows:

Subjects ≥ 4 years of age and weighing ≥ 10 to < 20 kg:

- Not taking a moderate or potent CYP3A4 inhibitor will receive a QD oral tolvaptan tablet dose of 3.75 mg, with possible up-titration to 7.5 mg and 15 mg
- Taking a moderate or potent CYP3A4 inhibitor are not eligible for optional tolvaptan treatment

Subjects weighing ≥ 20 to ≤ 50 kg:

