- Not taking a moderate or potent CYP3A4 inhibitor will receive a QD oral tolvaptan tablet dose of 7.5 mg, with possible up-titration to 15 mg and 30 mg
- Taking a moderate CYP3A4 inhibitor will receive half the starting tolvaptan tablet dose, eg, 3.75 mg tablet, with possible up-titration to 7.5 mg and 15 mg.
- Subjects are not eligible to receive optional tolvaptan treatment if they are taking a potent CYP3A4 inhibitor.

Subjects weighing > 50 kg

- Not taking a moderate or potent CYP3A4 inhibitor will receive a QD oral tolvaptan tablet dose of 15 mg, with possible up-titration to 30 mg and 60 mg
- Taking a moderate CYP3A4 inhibitor will receive half the starting tolvaptan tablet dose, ie, 7.5 mg, with possible up-titration to 15 mg and 30 mg

- Taking a potent CYP3A4 inhibitor will receive one quarter the starting tolvaptan tablet dose, eg, 3.75 mg, with possible up-titration to 7.5 mg and 15 mg.

Subjects not eligible for the optional tolvaptan treatment component still remain eligible for the core safety follow-up component.

Subjects eligible for the optional tolvaptan treatment component will titrate according to the guidelines listed in [Figure 3.2.1.2-1](#), targeting a final serum sodium concentration between 135 and 140 mEq/L (mmol/L). The clinician-directed target range is also acceptable.

Treatment can be discontinued at any time and cycles may be repeated as needed. If subjects are off tolvaptan treatment for ≥ 72 hours, re-initiation of tolvaptan treatment, starting with the pre-treatment baseline visit will occur. This will require a reassessment of the eligibility criteria, a tolvaptan titration period, and will begin in a hospital setting as part of a new treatment cycle.

The titration scheme is shown in [Figure 3.2.1.2-1](#).

[figure not shown]

Figure 3.2.1.2-1 Titration Scheme

Titration guidelines are designed to ideally achieve a change in serum sodium concentration of at least 4 to 8 mEq/L (mmol/L) /24 hours but not \geq 12 mEq/L (mmol/L)/24 hours.

Tolvaptan dose titration (after the initial dose) must be based on changes in serum sodium levels as follows:

- If the serum sodium level increases by \leq 4 mEq/L (mmol/L)/24 hours and the subject is still below the therapeutic target for serum sodium level (135 mEq/L [mmol/L]), then the tolvaptan dose may be titrated up to the next scheduled dose.

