3.8.3 Individual Subject Discontinuation

If a subject discontinues from the trial prematurely, the reason must be fully evaluated and recorded appropriately in source documents and the eCRF. If the subject is being withdrawn because of an AE, that AE should be indicated as the reason for withdrawal.

All subjects have the right to withdraw at any point during the trial without prejudice. The investigator can discontinue a subject's participation in the trial at any time if medically necessary. In addition, subjects meeting the following criteria must be withdrawn from tolvaptan treatment:

- a) Occurrence of any AE, intercurrent illness, or abnormality in a laboratory assessment which, in the opinion of the investigator, warrants the subject's permanent withdrawal of tolvaptan treatment;
- b) Treatment with a prohibited concomitant medication other than the use of appropriate medications for the treatment of AEs under direction of the investigator;
- c) Subject noncompliance, defined as refusal or inability to adhere to the trial schedule or procedures (see [Section 3.12](#), Subject Compliance);
- d) At the request of the subject, investigator, Otsuka Pharmaceutical Development & Commercialization, Inc. (OPDC) or designee, or regulatory authority;
- e) Subject becomes pregnant; or
- f) Subject is lost to follow-up.

In addition, subjects on tolvaptan treatment who meet the following criteria should have results confirmed with a repeat test. Sodium tests should be done either STAT or through bedside monitoring.

- The subject's serum sodium increases by > 8 mEq/L (mmol/L) in any 10-hour period following dosing on Day 1 of a cycle
- The subject's serum sodium increases by ≥ 12 mEq/L (mmol/L) in the 24-hour period following dosing
- At any time after dosing, the subject's serum sodium is ≥ 145 mEq/L (mmol/L).
- Evidence of dehydration
- Abnormal liver function tests (see [Section 5.4](#))

If the result is confirmed, the medical monitor should be contacted to consider options of down-titration, dose discontinuation, concomitant medication adjustment, fluid supplementation, and/or withdrawal.

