1.	Has evidence of hypovolemia or intravascular volume depletion (eg, hypotension, clinical evidence of volume depletion, response to saline challenge); if the subject has systolic blood pressure or heart rate outside of the normal range for that age volume status should be specifically clinically assessed to rule out volume depletion.
2.	Has serum sodium < 120 mEq/L (mmol/L), with or without associated neurologic impairment (ie, symptoms such as apathy, confusion, or seizures)
3.	Use of potent CYP3A4 inhibitors in subjects ≤ 50 kg or moderate CYP3A4 inhibitors in subjects < 20 kg
4.	Lacks free access to water (inability to respond to thirst) or without ICU-level fluid monitoring and management
5.	Has a history or current diagnosis of nephrotic syndrome
6.	Has transient hyponatremia likely to resolve (eg, head trauma or post-operative state)
7.	Has hyperkalemia defined as serum potassium above the ULN for the appropriate pediatric age range

Ineligibility Criteria for Tolvaptan Treatment	
8.	Has eGFR < 30 mL/min/1.73 m ² calculated by the following equation: eGFR (mL/min/1.73 m ²) = 0.413 × height (cm)/serum creatinine (mg/dL)
9.	Has acute kidney injury defined as: 
 • Increase in serum creatinine by ≥ 0.3 mg/dL (≥ 26.5 μmol/L) within 48 hours; or • Increase in serum creatinine to ≥ 1.5 times baseline, which is known or presumed to have occurred within the prior 7 days; or • Urine volume < 0.5 mL/kg/h for 6 hours
10.	Has severe or acute neurological symptoms requiring other intervention (eg, hyperemesis, obtundation, seizures)
11.	Has had treatment for hyponatremia with: 
 • Hypertonic saline (including normal saline challenge) within 8 hours of qualifying serum sodium assessments; • Urea, lithium, demeclocycline, conivaptan, or tolvaptan within 4 days of qualifying serum sodium assessments; • Other treatment for the purpose of increasing serum sodium concurrent with dosing of trial medication
12.	Has anuria or urinary outflow obstruction, unless the subject is, or can be, catheterized during the trial
13.	Has a history of drug or medication abuse within 3 months prior to the pretreatment visit or current alcohol abuse
14.	Has a history of hypersensitivity and/or idiosyncratic reaction to benzazepine or benzazepine derivatives (such as benazepril)
15.	Has psychogenic polydipsia (subjects with other psychiatric illness may be included per medical monitor approval)

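### Section 4.2 labels as prohibited the CYP3A4 inhibitors for which Section 3.2.1.2 sets reduced tolvaptan doses, so that under 3.8.3(b) the same child is both dosed and withdrawn

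*Protocol*

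**What the plan says.** Five places in the current protocol bear on a child who takes a CYP3A4 inhibitor.

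- **Section 3.2.1.2** treats the combination as a dosing matter: "Tolvaptan doses will be reduced 75% and 50% if a potent or moderate inhibitor, respectively, is being concurrently administered". For children above 50 kg it adds "Taking a potent CYP3A4 inhibitor will receive one quarter the starting tolvaptan tablet dose, eg, 3.75 mg" and "Taking a moderate CYP3A4 inhibitor will receive half the starting tolvaptan tablet dose, ie, 7.5 mg". Table 3.2.1.2-1 gives the full grid of starting doses.
- **Appendix 5, ineligibility item 3**, opens "Use of potent CYP3A4 inhibitors in subjects" and excludes potent inhibitors at 50 kg or below and moderate inhibitors below 20 kg. Other combinations are not excluded.
- **Section 4.1** is headed as a section on prohibited medications, but its text says that during treatment "continuous or short term use of other medications, while not prohibited, may be restricted by the investigator". It refers to Section 3.2.1 for dosing and then gives its only list, Table 4.1-1, a partial list of CYP3A4 inhibitors.
- **Section 4.2**, in its paragraph on saline, points back to Section 4.1 "for the partial list of prohibited medications during tolvaptan treatment".
- **Section 3.8.3(b)** names as a compulsory reason for stopping tolvaptan: "Treatment with a prohibited concomitant medication other than the use of appropriate medications for the treatment of AEs under direction of the investigator".

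**The concern.** Sections 3.2.1.2, 4.1 and Appendix 5 let some children on a listed inhibitor receive tolvaptan at a reduced dose. Section 4.2 gives the same list the label that Section 3.8.3(b) uses to trigger withdrawal. A site that follows the dose table treats the child. A site that follows 4.2 and 3.8.3(b) stops treatment. Each would be following explicit text.

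Inhibitor use is one of the three factors, with age and weight, that set a child's starting dose, and the trial population is paediatric. Whether a given co-medication means a smaller dose or no drug should not depend on the section a site happens to read.

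**Working it through.** There is no sample size, power or error-rate figure to reproduce. The check is a comparison of passages, plus the dose arithmetic.

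**Step 1: is the dose table consistent in itself?** The inputs are the starting doses without an inhibitor (3.75, 7.5 and 15 mg) and the reductions of 50% (moderate) and 75% (potent), all from Section 3.2.1.2. The formula is: reduced dose = starting dose × (1 − reduction).

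| Weight band (dose without inhibitor) | Moderate inhibitor | Potent inhibitor |
|---|---|---|
| 10 to below 20 kg (3.75 mg) | not eligible | not eligible |
| 20 to 50 kg (7.5 mg) | 7.5 × 0.50 = 3.75 mg | not eligible |
| above 50 kg (15 mg) | 15 × 0.50 = 7.5 mg | 15 × 0.25 = 3.75 mg |

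The three computed doses match the table. The three ineligible cells match Appendix 5 item 3. The contradiction is therefore not inside the dosing rules.

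**Step 2: what does the reference in Section 4.2 point to?** Section 4.1 contains one list, Table 4.1-1, and it holds CYP3A4 inhibitors. No other list of prohibited medications stands in 4.1, so Section 4.2 attaches its label to those inhibitors.

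**Step 3: follow one child through both routes.** Take a child above 50 kg on ketoconazole. The drug is in Table 4.1-1, and Section 1.2.1 calls it a potent CYP3A4 inhibitor.

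- Route A (4.1, 3.2.1.2, Appendix 5): not prohibited, not excluded at this weight, starts at 3.75 mg with possible up-titration to 7.5 and 15 mg.
- Route B (4.2, 3.8.3(b)): the drug is prohibited, so tolvaptan must be stopped.

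Ketoconazole is a cleaner example than conivaptan. Conivaptan is also listed, but it is separately restricted by Appendix 5 item 11, and Section 3.2.2 counts commercial vaptans as rescue therapy.

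**Step 4: count the affected cells.** The same two routes exist wherever the table carries a dose: 20 to 50 kg moderate, above 50 kg moderate, and above 50 kg potent. That is 3 of 6 cells. In the other 3 the child is ineligible under the dosing rules as well, so there is no dosed-versus-withdrawn conflict at the start of a cycle.

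**Step 5: an inhibitor started in mid-cycle.** Three texts apply and none is marked as governing.

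- Section 3.2.1.2 reduces the dose whenever an inhibitor is given concurrently, but the table it introduces is one of starting doses.
- The ineligibility criteria are reviewed at the pretreatment baseline visit of each cycle (Sections 3.1.2 and 3.7.3.2.1). The protocol does not say what follows if a child enters an excluded combination afterwards.
- Sections 4.2 and 3.8.3(b) together would withdraw the child.

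**The case against.** The best defence is that Section 4.2 contains a mis-aimed cross-reference and nothing more. The sentence sits in a paragraph about saline, and the amendment history shows that the reference was redirected to 4.1 from another section. Section 3.8.3(b) also keeps a meaning without the inhibitor list, because Section 4.2 itself prohibits grapefruit products, St. John's Wort, alcohol and hypertonic saline. This is a plausible account of how the conflict arose. It does not remove it: the section heading of 4.1, the label in 4.2 and the trigger in 3.8.3(b) all use the same word, and only the body of 4.1 says otherwise.

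A second defence is the exception in 3.8.3(b) for appropriate treatment of adverse events. It stands, and it narrows the conflict for some mid-cycle starts. It does not clearly cover a child already taking an inhibitor for an existing condition when the cycle begins, which is the case the starting-dose table addresses.

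Several stronger readings are tempting, and the documents do not support them.

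- A reader might infer from 4.1 a third outcome, a full unreduced dose. Section 4.1 refers to Section 3.2.1, which reduces the dose. There are two outcomes.
- A reader might multiply doses by the ketoconazole exposure ratios in Section 1.2.1 to size the hazard. At an unreduced dose that describes a breach of 3.2.1.2, which is a different matter from the contradiction. It also assumes proportionality, whereas Section 1.2.1 reports that 300 mg gave only 4.2-fold the peak concentration and 6.4-fold the steady-state AUC of 30 mg, a 10-fold dose difference.
- A reader might link mid-cycle starts to the rapid-correction endpoint. That endpoint covers the 24 hours after the first dose at introduction or reintroduction, so an inhibitor added later in a cycle falls outside it.
- A reader might conclude that Table 4.1-1 omits the moderate or potent class of each drug. The available text shows none, but a label could have been lost when the table was extracted, so this needs checking against the source.

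**Conclusion.** The contradiction is real and is in the current text. In 3 of the 6 weight-by-class combinations, Sections 3.2.1.2 and 4.1 with Appendix 5 item 3 lead to a reduced dose, while Sections 4.2 and 3.8.3(b) lead to withdrawal, subject to the adverse-event exception. The handling of mid-cycle starts is also unsettled.

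The conclusion rests on Table 4.1-1 being the only list in Section 4.1 that 4.2 can mean, which is so in the text available.

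A reader might also infer that the conflict blurs which sodium values count as on treatment and so touches the primary endpoint. SAP Sections 5.1 and 5.2 state that no subject received optional tolvaptan and that the analyses for that component will not be applied. No result is affected. The defect lies in the dosing instructions given to sites, and it would matter again if the text were reused.

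**What to change.** Reconcile Sections 3.2.1.2, 3.8.3(b), 4.1 (including its heading), 4.2 and Appendix 5 item 3, so that each weight band and inhibitor class has one stated status, in the same words everywhere. State whether that status also holds when an inhibitor is started after the pretreatment baseline visit. If the source table lacks it, mark each drug in Table 4.1-1 with the class that the dose table uses. Which rule holds is for the clinical team to decide.

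The cost is protocol wording in an amendment. No procedures, visits or subjects are added.

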5.1 Definitions

An AE is defined as any untoward medical occurrence in a patient or clinical trial subject administered a medicinal product and which does not necessarily have a causal relationship with this treatment. AEs would not include information recorded as medical

history at screening for pre-planned procedures for which the underlying condition was known and no worsening occurred. An adverse reaction is any untoward and unintended response to an IMP related to any dose administered.

A suspected adverse reaction is any AE for which there is a reasonable possibility that the IMP caused the AE. For the purpose of Investigational New Drug (IND) safety reporting, "reasonable possibility" means there is evidence to suggest a causal relationship between the IMP and the AE. Suspected adverse reaction implies a lesser degree of certainty about causality.

A serious adverse event (SAE) includes any event that results in any of the following outcomes:

- 1) Death
- 2) Life-threatening, ie, the subject was, in the opinion of the investigator or sponsor, at immediate risk of death from the event as it occurred. It does not include an event that, had it occurred in a more severe form, might have caused death.
- 3) Persistent or significant incapacity/disability or substantial disruption of the ability to conduct normal life functions
- 4) Requires in-patient hospitalization or prolongs hospitalization
 - Hospitalization itself should not be reported as an SAE; wherever possible the reason for hospitalization should be reported
 - Hospitalization or prolonged hospitalizations for social admissions (ie, those required for reasons of convenience or other non-medical need) are not considered SAEs
- 5) Congenital anomaly/birth defect
- 6) Other medically significant events that, based upon appropriate medical judgment, may jeopardize the subject and may require medical or surgical intervention to prevent one of the outcomes listed above, eg, allergic bronchospasm requiring intensive treatment in an emergency room or home, blood dyscrasias or convulsions that do not result in hospitalization, or the development of drug dependency or drug abuse.

Non-serious adverse events are all AEs that do not meet the criteria for a "serious" AE.

Immediately Reportable Event:

- Any SAE
- Any AE related to occupational exposure
- Potential Drug Induced Liver Injury (DILI) case (see [Section 5.4](#))
- Pregnancies are also defined as IREs. Although normal pregnancy is not an AE, it will mandate IMP discontinuation and must be reported on an

IRE form to OPDC. Pregnancy will only be documented on the AE eCRF if there is an abnormality or complication.

Clinical Laboratory Changes: It is the investigator's responsibility to review the results of all laboratory tests as they become available. For each abnormal laboratory test result, the investigator needs to ascertain if this is an abnormal (ie, clinically significant) change from baseline for that individual subject. (This determination, however, does not necessarily need to be made the first time an abnormal value is observed. The investigator may repeat the laboratory test or request additional tests to verify the results of the original laboratory tests.) If this laboratory value is considered medically relevant by the investigator (subject is symptomatic, requiring corrective treatment or further evaluation), or if the laboratory value leads to discontinuation, and/or fulfills a seriousness criterion, this is considered an AE.

Severity: Adverse events will be graded on a 3-point scale and reported as indicated on the eCRF. The intensity of an AE is defined as follows:

- 1 = Mild:** Discomfort noticed, but no disruption to daily activity.
- 2 = Moderate:** Discomfort sufficient to reduce or affect normal daily activity.
- 3 = Severe:** Inability to work or perform normal daily activity.

IMP Causality: Assessment of causal relationship of an AE to the use of the IMP is defined as follows:

- Related:** There is a reasonable possibility of a temporal and causal relationship between the IMP and the AE.
- Not Related:** There is no temporal or causal relationship between the IMP and the AE.

